7 PATIENTS AND SCREENING

In order to participate in this study the patients must meet all of the following inclusion criteria and must not meet any of the following exclusion criteria. Inclusion in the trial starts with the informed consent signature. Patients should only be permitted to screen for this study if they are free of any sub-clinical infection (indicated by the presence of an Eosinophil count below $0.3 \times 10^9/L$ within 1 month of screening). The inclusion and exclusion criteria are to be verified at the screening visit (Visit 1) and at the start of treatment/baseline visit (Visit 2).

7.1 Source of Patients

The study population will consist of male and female patients with confirmed diagnosis of AD aged 18 years or older. Patients will be identified and recruited by the investigational sites.

7.2 Inclusion Criteria

1. Patients with a clinically confirmed diagnosis of active AD according to Hanifin and Rajka criteria.
2. Patients with moderate to severe AD at baseline as defined by an IGA of minimum 3 at baseline.
3. Patients with an EASI score of ≥ 12 at screening and baseline.
4. Patients with AD covering a minimum 10% of the body surface area at baseline.
5. Patients whose pre-study clinical laboratory findings do not interfere with their participation in the study, in the opinion of the investigator.
6. Patients who are able and willing to stop all current treatments for AD throughout the study (except for allowed emollients).
7. Patients who are on a stable dose of a bland emollient applied BD (twice daily) for at least 7 days prior to baseline.
8. Male or female patients who are aged 18 years and older on the day of signing the informed consent form (ICF).
9. Female patients and male patients with female partners of child bearing potential must use adequate contraception or have a sterilized partner for the duration of the study. Adequate contraception is defined as: systemic hormonal contraceptives, intrauterine device or barrier method of contraception in conjunction with spermicide, or agree to sexual abstinence. Hormonal contraceptives must be on a stable dose for at least one month before baseline.
10. Patients who are able to communicate well with the investigator, to understand and comply with the requirements of the study, and understand and sign the written Informed Consent.

7.3 Exclusion Criteria

1. Patients with other skin conditions that might interfere with AD diagnosis and/or evaluation (such as psoriasis or current active viral, bacterial and fungal skin infections) as assessed by the investigator.

2. Patients who have used systemic treatments (other than biologics) that could affect AD less than 4 weeks prior to baseline visit (Day 0), e.g. retinoids, methotrexate, cyclosporine, hydroxycarbamide (hydroxyurea), azathioprine and oral/injectable corticosteroids. Intranasal corticosteroids and inhaled corticosteroids for stable medical conditions are allowed.
3. Patients who have used any topical medicated treatment for AD two weeks prior to start of treatment/ Baseline (Day 0), including but not limited to, topical corticosteroids, tars and bleach.
4. Patients who use topical products containing urea, ceramides or hyaluronic acid two weeks prior to Baseline.
5. Patients who use anti-histamines for AD within 2 weeks of baseline. Non-sedative anti-histamines for other indications may be used throughout the study provided the patient is on a stable dose for 4 weeks prior to Baseline.
6. Patients with the presence of an active or chronic allergic reaction as evidenced by an irregular white cell count determined by eosinophils $> 0.3 \times 10^9 /L$ at the screening visit.
7. Patients who have had excessive sun exposure, have used tanning booths or other ultraviolet (UV) light sources four weeks prior to Baseline (Day 0) and/or are planning a trip to a sunny climate or to use tanning booths or other UV sources between screening and follow-up visits.
8. Patients who have a history of hypersensitivity to any substance in DS107 capsules or placebo capsules.
9. Patients who have any clinically significant controlled or uncontrolled medical condition or laboratory abnormality that would, in the opinion of the investigator, put the patient at undue risk or interfere with interpretation of study results.
10. Patients who have a clinically significant impairment of renal or hepatic function.
11. Patients with significant uncontrolled cardiovascular, neurologic, malignant, psychiatric, respiratory or hypertensive disease, as well as uncontrolled diabetes and floride arthritis or any other illness that, in the opinion of the investigator, is likely to interfere with completion of the study.
12. Patients with chronic infectious disease (e.g., hepatitis B, hepatitis C or infection with human immunodeficiency virus).
13. Patients with a history of clinically significant drug or alcohol abuse in the opinion of the investigator in the last year prior to Baseline (Day 0).
14. Patients who have participated in any other clinical study with an investigational drug within 3 months before the first day of administration of study treatment.
15. Patients who have had treatment with biologics as follows:
 - a. Any cell-depleting agents including but not limited to rituximab: within 6 months before the screening visit, or until lymphocyte count returns to normal, whichever is longer,

- b. Other biologics influencing cell proliferation: within 6 months before the screening visit.
16. Patients who are pregnant, planning pregnancy, breastfeeding and/or are unwilling to use adequate contraception (as specified in inclusion criterion 9) during the trial.
17. Patients, in the opinion of the investigator, not suitable to participate in the study.

7.4 Screening and Consent

It is the responsibility of the investigator, or a person designated by the investigator (if acceptable to local regulation), to obtain written informed consent from each individual participating in this study after adequate explanation of the aims, methods, objectives and potential risks/benefits of the study. Patients will be given the opportunity to ask questions to the investigational team. It must also be explained to the patients that they are completely free to refuse to enter the study or to withdraw from it at any time for any reason. The patient will be given sufficient time to consider participation in the study. If, after this, the patient agrees to participate, they will be asked to sign and date one original copy of the written informed consent form (ICF). The patients will then receive a copy of the signed and dated patient information sheet (PIS)/informed consent form (ICF). The original signed ICF will be filed in the Investigator Site File (ISF). The PIS will contain site contact information in case of any questions or medical emergency.

If new safety information results in significant changes in the risk/benefit assessment or any new information presents that may affect willingness to continue to participate, the consent form should be updated and approved if necessary by the Research Ethics Board/Institutional Review Board. All patients (including those already being treated) should be informed of the new information, given a copy of the revised form and asked to give their consent to continue in the study. Any written information given to potential patients will be submitted to, and approved by, the respective Ethics Committee(s) (EC) prior to implementation.

The Investigator will maintain a Patient Screening Log to collect information on all patients who sign an ICF regardless of whether or not they meet the study eligibility criteria following completion of the screening evaluations. After completion of screening, all patients deemed eligible to take part in this study will be entered onto an Enrolment Log.

7.5 Withdrawal of Patients

Patients have the right to withdraw from the study at any time for any reason without penalty. The investigator must explain this to the patient and that this will in no way prejudice their future treatment. The investigator also has the right to withdraw patients from the study if he feels it is in the best interest of the patient or if the patient is uncooperative or non-compliant. It is understood by all concerned that an excessive rate of withdrawal can render the study uninterpretable, therefore, unnecessary withdrawal of patients should be avoided. Should a patient decide to withdraw, all efforts will be made to complete and report the observations, particularly the follow-up examination, as thoroughly as possible.

The investigator or one of his or her staff members should contact the patient either by telephone or through a personal visit to determine as completely as possible the reason for the withdrawal, and record the reason in patient's source document and CRF. A complete final early termination evaluation at the time of the patient's withdrawal should be made with an explanation of why the patient is withdrawing from the study. If the reason for removal of a patient is an adverse event or an abnormal laboratory test result, the principal specific event or test will be recorded. Patients who discontinue the study before Week 8/Visit 6 visit will be asked to come for an early termination visit as soon as possible and have the assessments listed at Week 8/Visit 6 performed. They will also be asked to return two weeks later for the safety assessments listed at Week 10/Visit 7.

There will be two main categories for withdrawals from the study: “complete withdrawal” and “withdrawals from investigational product”.

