7.5.1 Complete Withdrawal

Discontinuation of investigational product and all efficacy and safety evaluations. Standard reasons for withdrawing from further participation in the study and from the follow-up visits may be:

- Patients decision (withdrawal of consent to participate)
- Patient lost to follow-up (drop-out)

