7.5.2 Withdrawals from Investigational Product

Discontinuation of investigational product, but continued follow-up visits, including efficacy and safety evaluations. Standard reasons for withdrawing from taking further investigational product, but continuing follow-up visits and safety evaluations may be:

- Unacceptable adverse events
- Patient request
- Investigator’s discretion
- Intercurrent illness
- Lack of efficacy
- Pregnancy

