7.6 Patient Replacement

Patients who are withdrawn from the study due to an adverse event will not be replaced. Patients who are withdrawn for other reasons (such as lost to follow up, personal reasons) may be replaced.

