7.7 Protocol Violations

All protocol violations will be reviewed by the Medical Monitor as and when each violation is detected. Based on this review a decision on the patient’s continuation in the trial will be reached and this decision will be documented as appropriate. Notification will be made to the relevant authorities as required.

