8 STUDY CONDUCT

8.1 Study Schedule

During the study, six visits to the clinic are scheduled at least one week after the screening visit: one at the start of the comparative treatment period/baseline (Day 0/Visit 2) and five in the comparative treatment period (Week 2/Visit 3, Week 4/Visit 4, Week 6/Visit 5 and Week 8/Visit 6). A final safety follow-up visit (Visit 7) will be conducted two weeks after Visit 6 or two weeks after the final visit attended if the patient does not complete the study. The baseline visit must be performed, at the latest 30 days after the screening visit.

Patients who discontinue the study early will be asked to attend the investigative site as soon as possible so that assessments scheduled for Visit 6 can be conducted at an Early Termination visit.

In the event that treatment is occurring, a wash out period of up to 4 weeks may be necessary. At the Screening visit, after giving informed consent to participate, patients will be assessed using the screening examinations. Eligible patients with confirmed AD using the Hanifin and Rajka criteria and who meet all the inclusion criteria and do not meet the exclusion criteria at the baseline visit will be enrolled.

During the treatment period and follow-up period patients will be restricted from using any other treatment for AD, with the exception of the same emollients they have been consistently using at the baseline visit. Any medication (prescription as well as OTC drugs) or therapeutic intervention deemed necessary for the patient, and which in the opinion of the Investigator do not interfere with the safety and efficacy evaluations, may be continued. A list of ‘medications and therapeutic regimens excluded from the study’ is defined below (Section 9.2.11.2).

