8.2.7 Week 8 (Visit 6) / End of Treatment or Early Termination

Patients will return to the investigational site at Visit 6. **The last dose of DS107/Placebo should be taken the day before Visit 6.**

For accountability purposes, patients will be required to bring both the used DS107/Placebo patient packs and unused DS107/Placebo supplied at Visit 5. Patients will be required to provide the patient compliance log for confirmation of compliance.

The following procedures/assessments will occur:

- Samples for clinical laboratory safety tests (haematology, serum biochemistry, urinalysis as detailed in Section 9.2.4)
- Pharmacokinetic Sampling (as detailed in Section 9.2.7)
- Biomarker Sampling (as detailed in Section 9.2.8)
- Sample for pregnancy test (only female patients of child-bearing potential, as detailed in Section 9.2.5)
- Vital signs (blood pressures, heart rate and body temperature), as detailed in Section 9.2.3);
- Physical examination (as detailed in Section 9.2.2)
- Body Mass Index (as detailed in Section 9.2.6)
- Collect Study Drug
- Collect and Review Patient Compliance Log
- IMP Accountability (as detailed in Section 10.6)
- Body Surface Area (as detailed in Section 9.1.4)
- Investigator's Global Assessment (as detailed in Section 9.1.1)
- Eczema Area and Severity Index (EASI) (as detailed in Section 9.1.2)
- NRS Pruritus assessment (as detailed in Section 9.1.3)
- Dermatology Life Quality Index (DLQI) Questionnaire (as detailed in Section 9.1.5)
- Patient Orientated Eczema Measure (as detailed in Section 9.1.6)
- Patient Global Impression of Severity Questionnaire as detailed in Section 9.1.7)
- Patient Global Impression of Change Questionnaire as detailed in Section 9.1.8)
- Concomitant medication assessment (as detailed in Section 9.2.11)
- AE assessment (as detailed in Section 11)

The DS107or Placebo patient packs will be returned. No further DS107or Placebo patient packs or patient compliance logs will be issued. Following completion of the study assessments at this visit, there will be continued study restrictions in line with those described in sections 9.2.11 and 9.2.12.

An NRS for the assessment of pruritus will continue to be captured on a daily basis from baseline to the follow up visit. Emollient use will also continue to be captured on a daily basis for the same period.

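### An early-termination IGA can be analysed as the Week 8 response, and two withdrawal clauses can cost a consenting patient the Day 56 IGA

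*Protocol*

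**What the plan says.** **Week 8 visit.** Protocol 8.2.7 is headed "Week 8 (Visit 6) / End of Treatment or Early Termination", and the flow chart in Appendix 1 has a single Visit 6 column for both. Under Protocol 7.5, a patient who leaves before Visit 6 "will be asked to come for an early termination visit as soon as possible", and the Visit 6 assessments, IGA included, are done then. SAP 2.2.5 treats all seven visits as nominal for analysis. It places Visit 6 at Day 56 ± 2 for those who finish treatment, and at an unspecified earlier day for those who stop treatment. SAP 2.1 describes the end-of-therapy visit in a similar way, but ties the earlier date to leaving the study. SAP 2.2.6 names the outcome of its missing-data sensitivity analysis Week 8/Exit. Protocol 8.1 schedules the follow-up visit "two weeks after Visit 6 or two weeks after the final visit attended if the patient does not complete the study".

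**Withdrawal.** Protocol 7.5 lets the investigator withdraw people from the study in the interest of the "patient or if the patient is uncooperative or non-compliant". Under 7.7, the Medical Monitor reviews each violation and a decision on the patient's "continuation in the trial will be reached and this decision will be documented as appropriate". Section 7.5 then names two categories. Complete withdrawal (7.5.1) is "Discontinuation of investigational product and all efficacy and safety evaluations". Withdrawal from product (7.5.2) is "Discontinuation of investigational product, but continued follow-up visits, including efficacy and safety evaluations". Section 7.6 adds: "Patients who are withdrawn from the study due to an adverse event will not be replaced".

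**The concern.** The primary endpoint is IGA response at Week 8. If an ET assessment is stored under nominal Visit 6, the model in SAP 2.2.12.1, which has visit as a class effect and no rule about ET records, would take that IGA as Week 8 whatever day it was done. Protocol 6.1 expects the effect to build up and to peak over 4 to 6 weeks, so an earlier IGA measures something other than Week 8 response. One programmer could keep such records and another drop them, and both would be following the plan.

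The second, smaller issue is how these early records arise. If an investigator or Medical Monitor decision takes a consenting patient out of the study, no Day 56 IGA is scheduled. The endpoint is then either missing or represented by an early value. Loss that depends on compliance sits poorly with the missing-completely-at-random basis that SAP 2.2.6 states for its covariances and standard errors. The planned missing-data analyses would then be filling in outcomes that could have been observed.

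**Working it through.** **1. Can an early ET IGA be analysed as Week 8?**

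- Protocol 8.2.7 and Appendix 1: Week 8 and ET are one visit, Visit 6.
- SAP 2.2.5: analysis is by nominal visit, and Visit 6 may come early. The Day 56 ± 2 range is a visit schedule for completers; no analysis window is defined.
- SAP 2.2.5 links the early Visit 6 to stopping treatment, not to leaving the study. A patient on the 7.5.2 path, whose efficacy visits should go on, could therefore also have Visit 6 early.
- SAP 2.2.6: Week 8 and exit are joined in one label.
- SAP 2.2.12.1: the code and text contain no exclusion of ET records.

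Together these permit an early IGA in the Week 8 outcome. No sentence requires it and none forbids it.

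**2. Timing example (ET on Day 21 is assumed).** The IGA is 56 − 21 = 35 days early, at Week 3, before the 4 to 6 weeks of Protocol 6.1. Visit 7 under Protocol 8.1 falls near Day 21 + 14 = 35, not Day 70. SAP 2.1 first calls for an end-of-study visit for everyone, early leavers included, and then repeats the two-week return for early leavers, so it does not settle the date.

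**3. Which withdrawal path applies?**

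| Reason | 7.5.1, evaluations stop | 7.5.2, visits continue |
|---|---|---|
| Consent withdrawn, lost to follow-up | listed | not listed |
| Adverse event, patient request, investigator's discretion, intercurrent illness, lack of efficacy, pregnancy | not listed | listed |
| Non-compliance or lack of cooperation (7.5) | not listed | not listed |
| Protocol violation (7.7) | not listed | not listed |

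Both lists give possible reasons, so neither is closed. The gap is the last two rows. Neither the withdrawal sentence in 7.5 nor 7.7 refers to 7.5.2.

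**4. Can a size be put on it?** Protocol 12.3 gives 21.6% v 11.8%, 100 evaluable per arm and 45% power. Two-sided 5% z-test with pooled variance: mean rate 0.167; null SE = √(2 × 0.167 × 0.833/100) = 0.0527; alternative SE = √(0.216 × 0.784/100 + 0.118 × 0.882/100) = 0.0523; power = Φ((0.098 − 1.96 × 0.0527)/0.0523) = 45.9%, which agrees with the plan.

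No removal rate is given, so f = 5%, 10% and 20% are assumed:

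- Day 56 IGA lost, the rest responding at the arm rates: the difference stays at 9.8 points.
- Retained off product, active patients at the placebo rate (the reversion assumption in 12.9.2): (1 − f) × 21.6 + f × 11.8 − 11.8 = 9.3, 8.8 or 7.8 points.
- ET value used as Week 8 and always a non-response, equal f in both arms: (1 − f) × 9.8 = 9.3, 8.8 or 7.8 points, the same as retention.
- As above, with 20% removed on active and 5% on placebo: 0.80 × 21.6 − 0.95 × 11.8 = 6.1 points, against 7.8 if retained. Reversed: 0.95 × 21.6 − 0.80 × 11.8 = 11.1, against 9.3.
- Power: 44.0, 42.1 or 38.2% if values are lost; 42.6, 39.4 or 33.0% if patients are retained at the placebo rate.

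These figures show no bias. The gap between 9.8 and the retained figures (0.5, 1.0 or 2.0 points) compares two estimands: 9.8 is the de jure target that 12.9.2 makes primary, and the lower figures are the de facto one. The 1.8-point shifts come only from an unequal split chosen for illustration, and they change sign when it is reversed. Retention gives no power gain in this model.

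**The case against.** A reader might infer that the documents leave the withdrawal path open in general, or that 7.6 contradicts 7.5.2 on adverse events. They do not support that. Section 7.5 uses withdrawal from the study as the umbrella term for both categories, so 7.6 can be read consistently with 7.5.2. Adverse events and investigator's discretion are listed under continued visits, 11.4 lets a pregnant patient stay in the study off drug, and 7.5.1 lists only consent withdrawal and loss to follow-up. Removal for non-compliance could be seen as investigator's discretion. Some uncooperative patients would miss Day 56 under any wording, and 7.5 already discourages unnecessary withdrawal. This objection stands, and it narrows the withdrawal point to non-compliance, lack of cooperation and violation decisions.

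On the SAP side, a reader might infer that ET values are definitely counted as Week 8. The documents do not say so. SAP 2.2.5 ties Week 8 to Day 56 ± 2 for completers, SAP 2.2.6 says the model accounts for early withdrawal, and SAP 2.2.12.2 lists the last treatment visit as a separate analysis point. These suggest that early leavers were meant to be missing at Week 8. They are hints, though, and the visit definition in 2.2.5 points the other way.

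The plan also has missing-data analyses: jump-to-reference in Protocol 12.9.2 and extreme cases in SAP 2.2.6. They deal with values known to be missing, and an early IGA filed under Visit 6 would not be treated as missing.

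**Conclusion.** The point holds in two parts of unequal weight. The main part is that, as written, the SAP allows an ET IGA from well before Day 56 into the primary Week 8 outcome. This rests on the wording alone and needs no assumed rate. The smaller part is that 7.5 and 7.7 allow removal of a consenting patient for non-compliance, lack of cooperation or a violation without referring to 7.5.2, so the Day 56 IGA can be lost.

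No size of bias and no gain in power is claimed. A reader might take the illustrative differences as evidence of a biased treatment effect, but the documents give neither a removal rate nor any sign of differential loss between arms. The number analysed need not fall either: 12.3 counts evaluable patients, 7.6 allows replacement for reasons other than adverse events, and SAP 2.2.10 allows a larger sample after the interim analysis. The case for change is that the fix decides which IGA values enter the primary endpoint, and that this should be settled before unblinding.

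**What to change.** **SAP.** In 2.1 and 2.2.5, define the Week 8 value as the IGA at Day 56 ± 2, or within a stated analysis window around it. Give ET its own visit label. State that an ET IGA before that window is not analysed as Week 8 but may serve the last-treatment-visit analysis. In 2.2.6, replace Week 8/Exit with Week 8.

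**Protocol.** In 7.5 and 7.7, state that an investigator or Medical Monitor decision stops investigational product only, under 7.5.2. IGA and EASI visits then continue to Day 56 and Day 70 unless the patient withdraws consent, is lost to follow-up, or visits would be unsafe. Keep the ET visit for complete withdrawals. When to stop product stays with the investigator.

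**Analysis rule.** Flag each IGA taken off product or after prohibited treatment, and state in the SAP whether the primary GENMOD model uses it. Such values serve the de facto estimand of 12.9.2, not the de jure one, so the flag alone is not enough.

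**Cost.** Wording in both documents, one data flag, one analysis rule, and a few more visits that are already on the schedule and that some patients may decline. Patients with only an early ET IGA become missing at Week 8 and pass to the planned missing-data methods.
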